#### 8.3. Lost to Follow Up

A participant will be considered lost to follow-up if he or she repeatedly fails to return for scheduled visits and is unable to be contacted by the study site.

The following actions must be taken if a participant fails to return to the clinic for a required study visit:

- The site must attempt to contact the participant and reschedule the missed visit as soon as possible and counsel the participant on the importance of maintaining the assigned visit schedule and ascertain whether or not the participant wishes to and/or should continue in the study.
- Before a participant is deemed lost to follow up, the investigator or designee must make every effort to regain contact with the participant (where possible, 3 telephone calls and, if necessary, a certified letter to the participant's last known mailing address or local equivalent methods). These contact attempts should be documented in the participant's medical record.
- Should the participant continue to be unreachable, he/she will be considered to have withdrawn from the study with a primary reason of lost to follow-up.

## 9. STUDY ASSESSMENTS AND PROCEDURES

- Study procedures and their timing are summarized in the SoA.
- Protocol waivers or exemptions are not allowed
- Immediate safety concerns should be discussed with the sponsor immediately upon occurrence or awareness to determine if the participant should continue or discontinue study treatment.
- Adherence to the study design requirements, including those specified in the SoA, is essential and required for study conduct.
- All screening evaluations must be completed and reviewed to confirm that potential participants meet all eligibility criteria. The investigator will maintain a screening log to record details of all participants screened and to confirm eligibility or record reasons for screening failure, as applicable.
- Procedures conducted as part of the participant's routine clinical management (eg, blood count) and obtained before signing of ICF may be utilized for screening or

baseline purposes provided the procedure met the protocol-specified criteria and was performed within the time frame defined in the SoA.

- The maximum amount of blood collected from each participant over the duration of the study, including any extra assessments that may be required, will not exceed 500 mL.
- Repeat or unscheduled samples may be taken for safety reasons or for technical issues with the samples.

#### 9.1. Efficacy Assessments

#### 9.1.1. Induced Sputum samples

Participants should have pre-treatment with a short-acting bronchodilator prior to sputum induction where they have not conducted post-bronchodilator spirometry prior to sputum induction. Sputum induction will be performed using 3% saline given as 3 nebulisations [Singh, 2010]. Where 3% saline is insufficient to obtain a sufficiently large sputum sample, 4.5% saline will be administered as 3 nebulisations. This process may take from 10 to more than 20 minutes, depending on the participant and the concentration of salt. Sputum induction can be terminated at any time if participants are able to produce a sputum sample of sufficient volume. The participant should be monitored for 15 minutes following the procedure; if any respiratory distress or wheezing is present, a short-acting bronchodilator should be administered. Safety spirometry is required for 15 minutes after end of the procedure (see Section 9.4.5), and a short-acting bronchodilator should be administered of bronchospasm.

A minimum of 1ml of sputum will be collected. Remaining sputum may be stored for future biomarker analysis (see Section 9.1.2)

#### 9.1.2. Biomarkers

Sputum will be used to assess NET formation via a range of measures: Histone-elastase complexes, DNA-elastase complexes, NET area quantification by microscopy, ratio of sputum NETs to sputum neutrophils. Additionally, sputum will also be analyzed for resistin levels, elastase activity, microbiome composition and diversity and ex-vivo neutrophil phagocytosis of bacteria by flow cytometry, as samples permit.

Blood will be used for the assessment of NET formation in peripheral blood and to explore biomarkers associated with disease activity such as plasma fibrinogen and C-reactive protein (CRP).

Storage of biomarkers for future research is an optional part of this study, and participants will be asked for written consent for storage, which they can withdraw at any time. Blood, urine and sputum samples for biomarker research will be collected from participants in this study where possible as specified in the SoA.

Since collection of biomarkers is optional, separate collection procedures are not essential, i.e. sputum collection is through any remaining sputum from induction, and a further sputum induction is not necessary. Similarly, blood and urine will be collected for storage at the same time as taking clinical measurements for the study; where remnant volumes are insufficient for storage, further attempts at collection are entirely voluntary for participants.

In addition, with the participant's consent, samples will be stored and analysis may be performed on biomarker variants thought to play a role in NETosis to evaluate their association with observed clinical responses to danirixin.

Other samples may be used for research to develop methods, assays, prognostics and/or companion diagnostics related to danirixin, disease process, pathways associated with disease state, and/or mechanism of action of the study treatment.

#### 9.1.3. Measurement of volatile organic compounds (VOCs)

Exhaled breath samples through normal tidal breathing will be collected via a ReCIVA (Owlstone Medical, Cambridge, UK) collection device, which connects a disposable face mask onto multiple sorbent tubes that bind VOCs. The sorbent tubes will be stored and later subject to analysis via one or more devices that measure patterns of exhaled VOCs, such as eNoses or Field asymmetric ion mobility spectrometry (FAIMS) devices, and may also be subject to gas chromatography mass spectrometry for comparison. Exhaled breath samples should be collected at the timepoints specified in the SoA, and samples should be collected prior to administration of bronchodilators and sputum induction (with the exception of the samples taken at 4 hours post dose). Further sampling considerations are detailed in the SRM.

## 9.2. Adverse Events

The definitions of an AE or SAE can be found in Appendix 4.

The investigator and any designees are responsible for detecting, documenting, and reporting events that meet the definition of an AE or SAE and remain responsible for following up AEs that are serious, considered related to the study treatment or the study, or that caused the participant to discontinue the study treatment (see Section 8).

# 9.2.1. Time Period and Frequency for Collecting AE and SAE Information

- All SAEs will be collected from the signing of the ICF until the follow-up visit at the time points specified in the SoA (Section 2).
- All AEs will be collected from the signing of the ICF until the follow-up visit at the time points specified in the SoA (Section 2).
- Medical occurrences that begin before the start of study treatment but after obtaining informed consent will be recorded on the Medical History/Current Medical Conditions section of the CRF not the AE section.
- All SAEs will be recorded and reported to the sponsor or designee immediately and under no circumstances should this exceed 24 hours, as indicated in Appendix 4. The investigator will submit any updated SAE data to the sponsor within 24 hours of it being available.

- Investigators are not obligated to actively seek AEs or SAEs in former study participants. However, if the investigator learns of any SAE, including a death, at any time after a participant has been discharged from the study, and he/she considers the event to be reasonably related to the study treatment or study participation, the investigator must promptly notify the sponsor.
- The method of recording, evaluating, and assessing causality of AEs and SAEs and the procedures for completing and transmitting SAE reports are provided in Appendix 4

#### 9.2.2. Method of Detecting AEs and SAEs

Care will be taken not to introduce bias when detecting AEs and/or SAEs. Open-ended and non-leading verbal questioning of the participant is the preferred method to inquire about AE occurrence.

#### 9.2.3. Follow-up of AEs and SAEs

After the initial AE/SAE report, the investigator is required to proactively follow each participant at subsequent visits/contacts. All SAEs, and non serious AEs of special interest (as defined in Appendix 4) will be followed until the event is resolved, stabilized, otherwise explained, or the participant is lost to follow-up (as defined in Section 8.3). Further information on follow-up procedures is given in Appendix 4.

#### 9.2.4. Regulatory Reporting Requirements for SAEs

- Prompt notification by the investigator to the sponsor of a SAE is essential so that legal obligations and ethical responsibilities towards the safety of participants and the safety of a study treatment under clinical investigation are met.
- The sponsor has a legal responsibility to notify both the local regulatory authority and other regulatory agencies about the safety of a study treatment under clinical investigation. The sponsor will comply with country-specific regulatory requirements relating to safety reporting to the regulatory authority, Institutional Review Boards (IRB)/Independent Ethics Committees (IEC), and investigators.
- Investigator safety reports must be prepared for suspected unexpected serious adverse reactions (SUSAR) according to local regulatory requirements and sponsor policy and forwarded to investigators as necessary.
- An investigator who receives an investigator safety report describing a SAE or other specific safety information eg, summary or listing of SAE) from the sponsor will review and then file it along with the Investigator's Brochure and will notify the IRB/IEC, if appropriate according to local requirements.

#### 9.2.5. Cardiovascular and Death Events

For any cardiovascular events detailed in Appendix 4 and all deaths, whether or not they are considered SAEs, specific Cardiovascular (CV) and Death sections of the CRF will

be required to be completed. These sections include questions regarding cardiovascular (including sudden cardiac death) and non-cardiovascular death.

The CV CRFs are presented as queries in response to reporting of certain CV MedDRA terms. The CV information should be recorded in the specific cardiovascular section of the CRF within one week of receipt of a CV Event data query prompting its completion.

The Death CRF is provided immediately after the occurrence or outcome of death is reported. Initial and follow-up reports regarding death must be completed within one week of when the death is reported.

#### 9.2.6. Pregnancy

- Details of all pregnancies in female participants and, if indicated, female partners of male participants will be collected after the start of study treatment and until 60 hours after the end of treatment.
- If a pregnancy is reported, the investigator should inform GSK within 24 hours of learning of the pregnancy and should follow the procedures outlined in Appendix 5
- Abnormal pregnancy outcomes (eg, spontaneous abortion, fetal death, stillbirth, congenital anomalies, ectopic pregnancy) are considered SAE.

#### 9.3. Treatment of Overdose

For this study, any dose of danirixin greater than 70 mg within a 24-hour time period will be considered an overdose.

GSK does not recommend specific treatment for an overdose.

In the event of an overdose, the investigator/treating physician should:

- 1. Contact the Medical Monitor immediately.
- 2. Closely monitor the participant for AE/SAE, and laboratory abnormalities if applicable, for at least 3 days following overdose.
- 3. Obtain a plasma sample for PK analysis if requested by the Medical Monitor (determined on a case-by-case basis).
- 4. Document the quantity of the excess dose as well as the duration of the overdosing in the CRF.

Decisions regarding dose interruptions or modifications will be made by the investigator in consultation with the Medical Monitor based on the clinical evaluation of the participant.

#### 9.4. Safety Assessments

Planned time points for all safety assessments are provided in the SoA.

## 9.4.1. Physical Examinations

- A complete physical examination will include, at a minimum, assessments of the Skin, Cardiovascular, Respiratory, Gastrointestinal and Neurological systems. Height and weight (with participants wearing no shoes) will also be measured and recorded.
- Investigators should pay special attention to clinical signs related to previous serious illnesses.

#### 9.4.2. Vital Signs

- Pulse rate, respiratory rate, and blood pressure will be assessed.
- Seated blood pressure and pulse measurements will be assessed with a completely automated device. Manual techniques will be used only if an automated device is not available.
- Blood pressure and pulse measurements should be preceded by at least 5 minutes of rest for the participant in a quiet setting without distractions (eg, television, cell phones).
- Vital signs (to be taken before blood collection for laboratory tests) will consist of 1 pulse and 3 blood pressure measurements (3 consecutive blood pressure readings will be recorded at intervals of at least 1 minute). The average of the 3 blood pressure readings will be recorded on the CRF.

## 9.4.3. Electrocardiograms

- Triplicate 12-lead ECG will be obtained as outlined in the SoA using an ECG machine that automatically calculates the heart rate and measures PR, QRS, QT, and QTc intervals. Refer to Section 8.1.3 for QTc withdrawal criteria and additional QTc readings that may be necessary.
- At each time point at which triplicate ECG are required, 3 individual ECG tracings should be obtained as closely as possible in succession, but no more than 2 minutes apart. The full set of triplicates should be completed in less than 10 minutes.

## 9.4.4. Clinical Safety Laboratory Assessments

- Refer to Appendix 2 for the list of clinical laboratory tests to be performed and to the SoA for the timing and frequency.
- The investigator must review the laboratory report, document this review, and record any clinically relevant changes occurring during the study in the AE section of the CRF. The laboratory reports must be filed with the source documents. Clinically significant abnormal laboratory findings are those which are not associated with the underlying disease, unless judged by the investigator to be more severe than expected for the participant's condition.

- All laboratory tests with values considered clinically significantly abnormal during participation in the study should be repeated until the values return to normal or baseline or are no longer considered significantly abnormal by the investigator or medical monitor.
- If such values do not return to normal/baseline within a period of time judged reasonable by the investigator, the etiology should be identified and the sponsor notified.
- All protocol-required laboratory assessments, as defined in Appendix 2, must be conducted in accordance with the laboratory manual and the SoA.

# 9.4.5. Spirometry

Post-bronchodilator spirometry using FEV1 and FVC measurements (FEV1%pred, and FVC%pred and FEV1/FVC will be calculated based on Quanjer reference equations [Quanjer, 2012]) will be at time points listed in the SoA. Spirometry assessments should be performed in accordance with ATS/ERS guidelines as outlined in the SRM.

# 9.5. Pharmacokinetics

Blood samples for pharmacokinetic analysis of danirixin (approximately 1ml) will be collected at the time points indicated in SoA. The actual date and time of each blood sample collection will be recorded. The timing of PK samples may be altered and/or PK samples may be obtained at additional time points to ensure thorough PK monitoring. Processing, storage and shipping procedures are provided in the SRM.

Blood analysis will be performed under the management of Platform Technology and Science (PTS)/In vitro In Vivo Translation (IVIVT)/Third Party Resourcing (TPR), GlaxoSmithKline. Concentrations of DNX will be determined in the blood samples using the currently approved analytical methodology.

Raw data will be stored at the bioanalytical site (detailed in the SRM).

Once the blood has been analyzed for DNX, any remaining blood may be analyzed qualitatively for other circulating metabolites and the results reported under a separate PTS-IVIVT, GlaxoSmithKline protocol.

## 9.6. Genetics

A 6 mL blood sample for DNA isolation will be collected from participants who have consented to participate in the genetics analysis component of the study. Participation is optional. Participants who do not wish to participate in the genetic research may still participate in the study.

In the event of DNA extraction failure, a replacement genetic blood sample may be requested from the participant. Signed informed consent will be required to obtain a replacement sample unless it was included in the original consent. See Appendix 6 for Information regarding genetic research. Details on processes for collection and shipment and destruction of these samples can be found in the study reference manual.

## 9.7. Biomarkers

See Section 9.1.2 for information on biomarker collection and analysis.

# 9.8. Health Economics OR Medical Resource Utilization and Health Economics

Health Economics/Medical Resource Utilization and Health Economics parameters are not evaluated in this study.

# 10. STATISTICAL CONSIDERATIONS

# **10.1.** Sample Size Determination

Approximately 50 subjects will be enrolled in the study to obtain approximately 24 subjects who are randomized and also complete the primary endpoint assessment at Day 14. Subjects who are withdrawn may be replaced. Subjects will be randomized at a ratio of 3:1 for Danirixin:placebo.

While the sample size has been determined by feasibility, consideration has been made regarding the probability of observing a reduction in sputum NETs (quantified by Histone-elastase complexes). Observational data from an external cohort of COPD patients (not yet published) was used to quantify variability of the measurement and used for simulations. Other *ex vivo* data [Pedersen, 2017] using another CXCR2 receptor antagonist and a different assay method had demonstrated a 40% reduction in median spontaneous NET formation.

Danirixin effect is modelled through a parameter,  $\rho$ , which indicates the extent Danirixin attenuates the true mean sputum NETs value under treatment with placebo. If  $\rho = 1$ , then there is no Danirixin effect; if  $\rho < 1$ , then Danirixin reduces the mean sputum NETs value by that amount (e.g. if  $\rho = 0.7$  then Danirixin reduces mean sputum NETs by 30%.)

A mixture prior was utilized. One centred on no effect ( $\rho = 1$ ), the other centred on an effect with  $\rho = 0.7$ , with both normally distributed with the same standard deviation (0.182, based on historical data). It was assumed that under the no effect case, the probability that  $\rho$  is less than 0.7 is 5% and under the effect case, the probability that  $\rho$  is greater than 1.0 is 5%. The mixture prior used equal weight for each scenario.

Based on this prior, the following probabilities for the study were estimated:

• The probability to observe a mean Danirixin sputum NETs value, which is lower than that observed in the historical data set, is 69.3%.

• The study has a 70% probability of success of being at least 50% certain, after the study, that the true mean sputum NETs values for Danirixin are lower than Placebo

These estimates are contingent on assumptions about Danirixin effects; the ones selected are *a priori* plausible but may change once data from the study is available. Changes to sample size may be made based on the accruing information about effect size and variability once sufficient data is available.

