#### Number of Participants:

Approximately 50 participants will be screened to randomize 24 evaluable participants (18 in the treatment arm and 6 in the placebo arm). If a subject prematurely discontinues the study or is unable to complete all study assessments, additional subjects may be enrolled as replacement subjects at the discretion of the sponsor in consultation with the investigator. Additional subjects may be enrolled to improve the statistical properties of the end of study decision criteria (i.e., the probability of a positive outcome) based on the observed variability at an interim analysis. It is expected that the dropout rate in the study should be <10% given the study duration. Enrolment is not expected to exceed a maximum of 32 participants.

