# 5. STUDY DESIGN

## 5.1. Overall Design

[figure not shown]
A study schematic is shown in Figure 1. This is a parallel group study. Following screening, participants will be randomized (3:1) to receive danirixin 35 mg or placebo. Study treatment will be administered twice daily for 2 weeks.

Based on the observed variability at an interim analysis, additional subjects may be enrolled to improve the statistical properties of the end of study decision criteria (i.e., the probability of a positive outcome). Outputs containing unblinded treatment assignments will be created for this interim analysis will only be made available to a limited number of GSK staff. Full details will be included in the study data dissemination plan. No Independent Data Monitoring Committee (IDMC) will be utilized for this study.

While the study is being conducted, core members of the study team will be unblinded (with the exception of those study team members who will directly interact with study sites, e.g. Operations and Science Leader and Data Quality Leader). There will be ongoing review of safety data and clinical outcomes. Only the study statistician will have access to individual participant treatment assignments, other core team members will review aggregate summaries by study treatments. A study charter will specify which team members will have access to unblinded data while the study is ongoing and the data to be included in the data reviews.

The danirixin safety review team will perform ongoing safety review and will meet at least once while the study is ongoing and as needed based on emerging data to review available safety information.

• Follow up phone-call to occur within 7 days of last dose of study medication

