#### CONFIDENTIAL

treatment arm at Day 14. The posterior probability that the true mean reduction from baseline for the Danirixin treatment group in sputum NETs is greater than a 0%, 15%, 30% and 40% reduction will be calculated, as appropriate, depending on the observed data.

Additionally, the mean and corresponding 95% credible interval for the difference between Danirixin and placebo at Day 14 will be produced. The posterior probability that the true relative reduction from baseline in sputum NETs is greater than a 0%, 15%, 30% and 40% reduction will be calculated, as appropriate, depending on the observed data.

The existing reference data may be used to construct the prior distribution for the placebo arm instead of a non-informative prior. A non-informative prior will be utilized for the other parameters in the statistical model as appropriate to their distribution.

Other efficacy data will be presented in tabular and/or graphical format and summarized descriptively. Full details of the analyses to be performed on all efficacy endpoints will be described in the reporting and analysis plan (RAP).

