2. SUMMARY OF KEY PROTOCOL INFORMATION

2.1. Changes to the Protocol Defined Statistical Analysis Plan

Protocol	Reporting & Analysis Plan	
Statistical Analysis Plan	Statistical Analysis Plan	Rationale for Changes

 Enrolled - All participants who sign informed consent 	
 Enrolled - All participants who sign informed consent and for whom a record exists on the study database 	
 Align with standard Enrolled population definition.

 Randomised 	
 mITT population defined to be used for selected displays 	
 Used for key displays

 Primary completer 	
 Population definition refined 	
 To allow for missing data and increase clarity

 Safety 	
 mITT population used for safety reporting 	
 Safety population not required.

 PK population 	
 PK population defined 	
 Used for PK displays

 Endpoint - Model specific PK parameters of danirixin (e.g., oral clearance, oral steady state volume of distribution). 	
 Danirixin concentration and standard pharmacokinetic (PK) parameters for danirixin (e.g. AUC, Cmax, tmax) 	
 Updated due to small number of participants with PK data

 Endpoints - serum IL-8 or sputum mucin 	
 Removed 	
 Not collected

 Primary analysis Bayesian 	
 Primary analysis Frequentist 	
 The primary analysis has been simplified as the historical data could not be used as a prior.

 Modified Primary Completer 	
 Population defined 	
 Defined to allow for a sensitivity around the definitions of quality for the samples

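### Does the 70% probability of success in Protocol 10.1, built on a 50% certainty bar, need to be recalculated or split?

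*Protocol*

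**What the plan says.** Protocol 10.1 says the sample size rests on feasibility, then describes two simulated probabilities. Danirixin's effect is a multiplier ρ on the mean sputum NETs value under placebo. The design prior is an equal mixture of a component centred on ρ = 1 and one centred on ρ = 0.7, "both normally distributed with the same standard deviation (0.182, based on historical data"). The next sentence sets a 5% tail beyond 0.7 in the first component and beyond 1.0 in the second. Two results follow: "The probability to observe a mean Danirixin sputum NETs value, which is lower than that observed in the historical data set, is 69.3"%, and "The study has a 70% probability of success of being at least 50% certain, after the study, that the true mean sputum NETs values" are lower for danirixin than for placebo. The section adds that both depend on the assumed effects.

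Protocol 10.3.1 covers the priors for the analysis itself: "The existing reference data may be used to construct the prior distribution for the placebo arm instead of a non-informative prior". And: "A non-informative prior will be utilized for the other parameters in the statistical model as appropriate to their distribution". SAP 2.1 then replaces the Bayesian primary analysis with a frequentist one: "The primary analysis has been simplified as the historical data could not be used as a prior".

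On extra recruitment, Protocol 5.1 looks to the variability seen part-way through the study and says this: "additional subjects may be enrolled to improve the statistical properties of the end of study decision criteria (i.e., the probability of a positive outcome"). The Synopsis adds: "Enrolment is not expected to exceed a maximum of 32 participants".

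**The concern.** A reader used to power calculations may take 70% as the chance that the study detects a working drug. It is not that. It averages over a prior that already favours benefit, and it counts success at a bar which an inactive drug clears about as often as a coin lands heads. Neither published probability shows how often an ineffective drug would look successful, or how often a 30% reduction would be recognised.

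Three further points seem to add weight. The same figure could be taken as the target for extra enrolment, although it barely responds to sample size. The SAP drops the historical data as a prior without restating the 70%. And 0.182 is attributed to historical data, yet it can be derived from the 5% tail assumption alone. If all this held, the design would rest on a figure that is uninformative and perhaps no longer attainable.

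**Working it through.** **Inputs.** From Protocol 10.1: component centres 1 and 0.7, SD 0.182, weights 0.5 and 0.5, stated results 69.3% and 70%. From the Synopsis: 18 danirixin and 6 placebo, with a cap of 32 (24:8 at the 3:1 ratio). Not in the documents: the outcome SD, the size of the historical cohort, and the correlation between baseline and Day 14. Standard errors (SE) below are in units of the placebo mean.

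**Prior SD.** 0.3/1.645 = 0.182, so the tail assumption alone yields the stated value.

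**Probability of benefit under the design prior.** P(ρ<1) = 0.5 × 0.5 + 0.5 × Φ(0.3/0.182) = 0.25 + 0.5 × 0.950 = 0.725.

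**What the 50% bar means.** With a non-informative analysis prior and roughly symmetric error, a posterior probability of at least 50% is the same event as an estimate favouring danirixin. The averaged success probability is then

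A(SE) = 0.25 + 0.5 × Φ(0.3/√(0.182² + SE²)),

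which runs from 0.50 (SE very large) to 0.725 (SE near zero).

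**The plan's own figures.**
- SE = 0.147: √(0.0331 + 0.0217) = 0.234; Φ(0.3/0.234) = 0.900; A = 0.25 + 0.45 = 0.700.
- SE = 0.170: √(0.0331 + 0.0288) = 0.249; Φ(0.3/0.249) = 0.886; A = 0.693.

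Both are consistent with the stated prior. They cannot be reproduced independently without the SD. Of the 70 points, 25 come from the no-effect component.

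**Pass rate for an inactive drug.** At ρ = 1 it is Φ(0) = 50%, whatever the SE. A lognormal simulation at 18:6 (assumed CV 0.5 to 1.0) gave 50% on the log scale and 45–48% on arithmetic means. If the mixture had also been the analysis prior, an inactive drug would pass 62–79% of the time and the average would be 75–85% for SE 0.147 to 0.339. That does not match 70%, so the non-informative reading fits better, although 10.1 does not say which prior was used.

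**Without the historical prior.** Assume that 69.3% compares 18 danirixin patients with n_h historical patients, with equal SDs and unadjusted means. Then 0.170² = CV² × (1/18 + 1/n_h).

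| n_h | CV | SE at 18:6 | A at 18:6 | A at 24:8 | pass rate at ρ = 0.7, 18:6 |
|---|---|---|---|---|---|
| 10 | 0.43 | 0.203 | 68.2% | 69.1% | 93% |
| very large | 0.72 | 0.339 | 64.1% | 65.4% | 81% |

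These are the source of the 64–68% range and of the shift of about 1 point from extra enrolment.

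**Sensitivity to the model.** The planned analysis is a repeated-measures model, which in SAP 7.1.5.1 adjusts for baseline. With simple adjustment, SE² is multiplied by 1 − r². Reaching A = 69.5%, which rounds to 70%, needs SE = 0.163:
- n_h = 10: 1 − r² = (0.163/0.203)², so r is about 0.59.
- n_h very large: 1 − r² = (0.163/0.339)², so r is about 0.88.

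No correlation is given, so the documents neither support nor exclude a shortfall. Over an assumed unadjusted SD of 0.2 to 1.2, the pass rate at ρ = 0.7 runs from 99.9% to 70%. It cannot be fixed from outside.

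**The case for a change.** The strongest case is that the core needs no missing input. The 50% pass rate at ρ = 1 and the 72.5% ceiling follow from the protocol's own text. The sponsor chose to publish a probability of success, and one rerun of an existing simulation would let readers see the two scenarios separately. Protocol 5.1 speaks of improving the chance of a positive outcome, and the 70% is the published figure closest to that phrase. A frequentist estimate that merely favours danirixin is the same coin-toss event, so the change of method does not remove the issue.

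The arithmetic stands in full, and so does the warning against reading 70% as power. The rest carries less weight:

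- **Use of the figure.** No passage makes 50% certainty a decision rule. Protocol 10.3.1 already plans credible intervals and posterior probabilities for reductions beyond 0%, 15%, 30% and 40%. SAP 2.4 and 5.4 plan estimation without testing.
- **Enrolment.** Protocol 5.1 ties extra recruitment to observed variability. Protocol 10.3.5 ties it to the posterior probability of a reduction within the danirixin arm. Neither names the prior-averaged comparison with placebo. SAP 2.3 and 3.1 drop the formal interim analysis, and the rise to about 30 was to replace 6 participants with poor-quality data.
- **Loss of the historical prior.** The 64–68% range uses unadjusted single means and a back-solved CV. Protocol 10.3.1 made borrowing optional, and 10.1 does not say whether the 70% relied on it.
- **Source of 0.182.** This is a point of wording. The value is the same on either reading and no result moves.

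**Conclusion.** No change follows. The 70% is a weak summary, but its ingredients are openly stated (the bar, both components, the weights and the SD), it is consistent with the stated prior, and it determined neither the sample size nor any decision rule. Firm results: P(ρ<1) = 72.5%; under a non-informative analysis prior with roughly symmetric error, an inactive drug meets the bar about 50% of the time at any sample size; the averaged figure lies between 50% and 72.5%. Not established: that 70% is unattainable with six concurrent placebo patients, since this depends on an outcome SD, a historical cohort size and a baseline correlation that are not given.

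Splitting the figure by scenario, adding stricter thresholds or sourcing 0.182 would be extra description. SAP 3.2 records that the study stopped early with 19 completers, and SAP 2.1 makes the primary analysis frequentist. A rerun at 18:6 with posterior thresholds would therefore describe a design and an analysis no longer in use, and would alter no estimate, interval or conclusion.
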